5.5. Secondary Endpoint(s) Analysis

5.5.1. Definition of Endpoint(s)

The following endpoints will assess the humoral immune response to 3 dose levels of Ad26.COV2.S (2.5×10^{10} vp, 1.25×10^{10} vp or 0.625×10^{10} vp) in all participants (Part 1) in all study groups, at all blood collection timepoints:

- Binding antibody titers to SARS-CoV-2 or individual SARS-CoV-2 proteins (eg, S protein) as measured by ELISA (or equivalent assay),
and/or
- Neutralizing antibody titers to SARS-CoV-2 as measured by VNA titers.

5.5.2. Estimand(s)

Not applicable

5.5.3. Analysis Methods

The analysis methods are described in Section [5.8.1](#).

5.6. Exploratory Endpoint(s) Analysis

Definitions and details about the analysis methods for exploratory humoral immunogenicity endpoints are given in Section [5.8.1](#). Some of the exploratory immunogenicity endpoints mentioned in this section will only be considered as potential assessment for post-hoc analysis after the primary analysis is performed, as described in Section [1.1](#).

Immune response in vaccinated adolescents after natural SARS-CoV-2 infection.

- Confirmation of SARS-CoV-2 infection by molecular testing.
- SARS-CoV-2 neutralizing titers in serum measured by a VNA.
- SARS-CoV-2-binding antibodies measured by ELISA: Analysis of antibodies binding to the SARS-CoV-2 S and/or N-protein. Infections in this study were identified either by a positive PCR test or by N serology seroconversion (N-ELISA result from negative to positive) [see Section [5.8.3](#)]. In order to censor data from participants following a potential SARS-CoV-2 infection not identified by the pre-defined infection rule, a sensitivity analysis will be performed on vaccine-induced humoral responses (binding and neutralizing antibody titers) for the PPI at the time of the final analysis. In this sensitivity analysis, data from participants from the time point where a ≥ 2 -fold increase in N-ELISA titers is observed in any two consecutive available time points during the study will be censored.

Correlation (at selected timepoints)

- ELISA (S-ELISA; EU/mL, or equivalent assay) and VNA (wtVNA and/or psVNA) titers
 - For S-ELISA and wtVNA correlation.
 - For S-ELISA and psVNA correlation.
- ELISA (S-ELISA; EU/mL, or equivalent assay) titers at baseline and its fold increase from baseline.

Occurrence of symptomatic molecularly confirmed COVID-19 and severity of COVID-19 signs and symptoms in adolescents

- The number of adolescents with molecularly confirmed COVID-19.
- Presence and severity of COVID-19 signs and symptoms as measured by the Symptoms of Infection with Coronavirus-19 (SIC).

Occurrence of asymptomatic SARS-CoV-2 infection

- Serologic conversion between baseline (Day 1; pre-vaccination) and selected timepoints post-vaccination using an ELISA and/or SARS-CoV-2 immunoglobulin assay that is dependent on the SARS-CoV-2 N protein
- The number of asymptomatic participants with a SARS-CoV-2 positive molecular test.

For asymptomatic case definition, see CTP (Section 10.9.3).

Impact of pre-existing humoral immunity against coronaviruses other than SARS-CoV-2 at baseline on Ad26.COV2.S vaccine immunogenicity

- Analysis of antibodies binding to coronaviruses other than SARS-CoV-2 by ELISA or equivalent assay.

Impact of the Ad26.COV2.S vaccine on the incidence of co-infections with SARS-CoV-2 and other respiratory pathogens in adolescents who have received Ad26.COV2.S during the study.

- Analysis of broad respiratory pathogens panel in the nasal swabs collected during a confirmed COVID-19 episode and in nasal swab samples from adolescents with a symptomatic infection.

SARS-CoV-2 variants during a confirmed COVID-19 episode in adolescents

- Identification of SARS-CoV-2 variants by sequencing of nasal swabs and/or saliva samples (as available) collected during a confirmed COVID-19 episode.

SARS-CoV-2 viral load during a confirmed COVID-19 episode in adolescents

- Analysis of SARS-CoV-2 viral load (via qRT-PCR) in nasal swabs and/or saliva samples (as available) collected during a confirmed COVID-19 episode.

Explore the humoral immune response in participants who have received Ad26.COV2.S.

Exploratory analyses may include the following:

- SARS-CoV-2 neutralization as assessed by VNA.
- Adenovirus neutralization as measured by VNA.
- Functional and molecular antibody characterization including, but not limited to avidity, Fc-mediated viral clearance, Fc characteristics, Ig subclass and IgG isotype, antibody glycosylation, and assessment of antibody repertoire.
- Analysis of antibodies to S, N, and the RBD of the SARS-CoV-2 S protein, and surface proteins of other coronaviruses.

- Epitope-specificity characterization of antibodies.
- Cytokine profiling: Analysis of cytokines, chemokines, and other proteins of the innate or adaptive immune response in the serum or plasma.
- Passive transfer: Analysis of immune mediators correlating with protection against experimental SARS-CoV-2 challenge in a suitable animal model.

5.7. (Other) Safety Analyses

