2. STATISTICAL HYPOTHESES

There is no formal hypothesis testing in Part 1.

Descriptive statistics will be reported to descriptively compare vaccine immunogenicity in adolescents from this study VAC31518COV3006 versus vaccine immunogenicity in selected young adults (18 to 25 years of age) from study VAC31518COV3001 or study VAC31518COV3009 (with similar baseline characteristics to the participants expected to be enrolled in this study – see Section 6.11), and between study groups in VAC31518COV3006.

All enrolled participants were seronegative for SARS-CoV-2 antibodies when screened with local rapid finger-prick serology testing at baseline. However, the primary analysis results have shown that many participants were retrospectively established to be SARS-CoV-2 seropositive at baseline by central testing with Nucleocapsid (N) and/or Spike (S) -based serology. Therefore data from SARS-CoV-2 seropositive young adult (18 to 25 years of age) selected from other Phase 3 studies will be used to compare vaccine immunogenicity in seropositive at baseline adolescents from this study.

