5. STATISTICAL ANALYSES

5.1. General Considerations

Details of the vaccine schedules associated to the primary vaccine regimen will be provided in the data presentation specification (DPS) document. Vaccination schedule have 2 components:

- Primary Vaccine Regimen (1-active dose or 2-active dose)
- Booster Vaccination (i.e. after unblinding)

Unless specified otherwise, analyses outputs will be produced by age group (12 to 15, 16 to 17, and overall). Where applicable, output will include results by dose level (1-active dose regimen and 2-active dose regimen combined) to report the post-dose 1 period.

All safety and immunogenicity data after a participant has received any other SARS-CoV-2 vaccine not part of the protocol will not be tabulated. Those data will be in listings.

A baseline (or reference) value will be defined as the value of the last available assessment prior to the first vaccination on Day 1, unless specified otherwise.

Unless otherwise stated, safety analyses will be conducted on the FAS, Immunogenicity analyses on the PPI.

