5.1.6. Analyses by Groups and Pooled Across Groups

In Part 1, summary outputs will be produced with pooled study groups that received the same dose up to D57 in addition to the analyses planned for each study group separately, unless specifically indicated otherwise. Immunogenicity analyses will be carried out by SARS-CoV-2 serostatus at baseline (in participants with a baseline result by central N- and S- serology testing, in PPI or FAS) and 'overall' (all participants, in PPI or FAS).

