5.8.1.2. Handling of Missing and/or Unquantifiable Immune Response Data

Missing immune response data will not be imputed.

Values below the lower limit of quantification (LLOQ) or limit of detection (LOD, if available instead of LLOQ) will be handled as follows:

- Calculation of geometric mean and median:
 - values <LLOQ are imputed with LLOQ/2.
- Calculation of fold increases from baseline:
 - values <LLOQ are imputed with LLOQ.

Values above the upper limit of quantification (ULOQ) will be handled as follows:

- Calculation of geommean and median:
 - Values >ULOQ are imputed with ULOQ.
- Calculation of fold increases from baseline:
 - Values >ULOQ are imputed with ULOQ.

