The ratio of binding antibodies (S-ELISA or equivalent assay, e.g. MSD) to wild type VNA, and the ratio of binding antibodies (S-ELISA or equivalent assay, e.g. MSD) to pseudovirion expressing S protein VNA will be calculated for each time point. Values <LLOQ will be imputed with LLOQ for the calculation of the ratios. In addition, the ratio of the fold increase from baseline in binding antibodies (S-ELISA or equivalent assay, e.g. MSD) to the fold increase from baseline in wild type VNA, and the ratio of the fold increase from baseline in binding antibodies (S-ELISA or equivalent assay, e.g. MSD) to the fold increase from baseline in pseudovirion expressing S protein VNA will be calculated for each post-baseline time point. Values <LLOQ will be imputed with LLOQ for the calculation of the fold increase ratios. The following statistics will be calculated and tabulated: N, geometric mean and corresponding 95% CI of the ratio. Graphical displays will also be prepared, showing – for each time point – the geometric mean of the ratio and its 95% CI, together with the individual data points (dot plot).

If a similar assay is performed at different analyzing labs, then separate statistical analyses may be performed.

Scatterplots between humoral assay results will be provided for selected time points. These may include but are not limited to:

- Binding antibodies S-ELISA (or equivalent assay) versus VNA (wtVNA and/or psVNA)
- Ad26 VNA versus S-ELISA (or equivalent assay), wtVNA or psVNA (as available)

If a similar assay is performed at different analyzing labs, then the statistical analyses may distinguish between these and provide separate scatterplots for each analyzing lab versus the other assay of interest. These scatterplots will display the values as analyzed for the geometric mean calculations, with values <LLOQ imputed with LLOQ (if an LLOQ is defined) and values >ULOQ imputed with ULOQ (if an ULOQ is defined). The LLOQ and ULOQ cut-off values per assay will

be visualized in the scatterplots. Spearman correlation coefficients will also be provided (one per scatterplot).

Further details and/or updated rules will be provided in the DPS.

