5.8.4. Demographics and Baseline Characteristics

Demographic and baseline variables will be summarized by vaccination schedule and overall for the FAS. Details about demographics and baseline characteristics are provided in Section [6.4](#).

SARS-CoV-2 Serostatus at baseline will be derived from the S-ELISA, N-ELISA as well as from MSD 4, if available. Seronegative at baseline is defined as negative per S-ELISA and per N-ELISA (values \leq LLOQ) and, if available, per MSD 4plex S and MSD 4plex N (values \leq LOD or LLOQ*). Seropositive at baseline is defined as positive per S-ELISA or per N-ELISA (values $>$ LLOQ), or, if available, per MSD 4plex S or per MSD 4plex N (values $>$ LOD or LLOQ*). SARS-CoV-2 Serostatus at baseline will be assigned to ‘no baseline’ if the S-ELISA or N-ELISA results are missing. Since MSD 4 results were not available by the time of the primary analysis, and the same derivation rules will be applied for the final analysis, SARS-CoV-2 Serostatus at baseline will be derived from the S-ELISA, N-ELISA only.

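### Baseline S-ELISA is to be correlated with its own fold increase, so the coefficient is negative even when baseline is unrelated to the post-vaccination titre

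*SAP*

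**What the plan says.** SAP 5.6, under its correlation heading and for selected timepoints, pairs S-ELISA with VNA and then adds "ELISA (S-ELISA; EU/mL, or equivalent assay) titers at baseline and its fold increase from baseline". SAP 5.1 fixes what baseline means: "A baseline (or reference) value will be defined as the value of the last available assessment prior to the first vaccination on Day 1". Section 5.6 gives no other reference point for this bullet, so one measurement supplies both the baseline titre and the denominator of the fold increase.

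On the coefficient, SAP 5.8.1.4.1 states for its scatterplots of humoral assay results: "Spearman correlation coefficients will also be provided (one per scatterplot". For fold increases, SAP 5.8.1.2 says "values <LLOQ are imputed with LLOQ" at the lower end and "Values >ULOQ are imputed with ULOQ" at the upper end.

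Two further statements bear on the reading. SAP 2 reports that "many participants were retrospectively established to be SARS-CoV-2 seropositive at baseline by central testing", and SAP 5.1.6 says "Immunogenicity analyses will be carried out by SARS-CoV-2 serostatus at baseline" as well as overall. Neither document mentions the shared baseline term, a reference value other than zero, or an adjustment.

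**The concern.** On the log scale a fold increase is post-vaccination titre minus baseline titre. Correlating baseline with that difference puts baseline, with a minus sign, into the second variable. Zero is then not the value expected when baseline and post-vaccination titre are unrelated.

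This matters because of who was enrolled. With many participants seropositive by central testing, baseline titres vary, and how prior antibody relates to the response is a natural question. A reader who sees a coefficient of about -0.6 may conclude that pre-existing antibody blunts the response. The same number can arise when the post-vaccination titre does not depend on baseline at all.

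**Working it through.** The plan states no value for this coefficient, so there is no figure to reproduce.

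**Inputs.** From the documents: the pair of variables (SAP 5.6), the definition of baseline (SAP 5.1), the LLOQ and ULOQ rules (SAP 5.8.1.2), the serostatus definition (SAP 5.8.4) and 50 participants per group (SAP 3). Assumed: the ratio of baseline to post-vaccination SD and the share of seropositive participants, shown as ranges because the documents give neither.

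**Formula.** Let X = log10 baseline, Y = log10 post-vaccination titre, k = SD(X)/SD(Y) and r = corr(X, Y). Then

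corr(X, Y - X) = (r - k) / sqrt(1 + k² - 2rk).

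The sign is that of r - k. The slope of Y on X is r/k, so the coefficient is negative if the slope is below 1, zero if it equals 1 and positive if it exceeds 1. For bivariate normal data, Spearman = (6/π)·asin(Pearson/2). Taking logs does not change ranks.

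**No relation (r = 0).** The formula becomes -k/sqrt(1 + k²). At k = 1 this is -1/√2 = -0.71, and Spearman is (6/π)·asin(-0.354) = -0.69.

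| k (baseline SD / post SD) | Pearson | Spearman |
|---|---|---|
| 0.25 | -0.24 | -0.23 |
| 0.5 | -0.45 | -0.43 |
| 0.75 | -0.60 | -0.58 |
| 1 | -0.71 | -0.69 |
| 1.5 | -0.83 | -0.82 |
| 2 | -0.89 | -0.89 |

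In simulated groups of 50 with no relation, the central 95% of Spearman values ran from -0.82 to -0.50 at k = 1, and from -0.64 to -0.18 at k = 0.5.

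**True positive relation.** With r = 0.5 and k = 1 (slope 0.5), the coefficient is (0.5 - 1)/sqrt(1 + 1 - 1) = -0.50. With r = 0.5 and k = 0.5 (slope 1) it is 0. With r = 0.75 and k = 0.5 (slope 1.5) it is +0.35.

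**Baselines at the LLOQ.** Simulation, no relation, seronegatives set to LLOQ. Seropositive log10 baselines were centred 0.5 to 0.8 above LLOQ with SD 0.3 to 0.5; post-vaccination SD was 0.5 to 0.6 (all assumed).

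| Share seropositive | Spearman, overall |
|---|---|
| 5% | -0.19 to -0.26 |
| 20% | -0.37 to -0.49 |
| 50% | -0.52 to -0.69 |
| 80% | -0.54 to -0.73 |

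Among seropositives alone the range was -0.49 to -0.68. In the same data sets, baseline against the post-vaccination titre itself gave -0.007 to 0.004.

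**Post-vaccination values at the ULOQ.** At k = 1, capping half of the post-vaccination titres moved the no-relation Spearman from -0.69 to -0.87.

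**Seronegative stratum.** SAP 5.8.4: "Seronegative at baseline is defined as negative per S-ELISA and per N-ELISA", that is, both at or below LLOQ. After the LLOQ rule, baseline S-ELISA is constant there and no coefficient can be computed.

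**The case against.** The best defence is that the statistic answers a real question: is the fold rise constant across baseline? If every participant has the same expected fold rise, the coefficient is 0. If post-vaccination titre is unrelated to baseline, fold rise truly is smaller at higher baseline, and a negative value describes that correctly; only the part due to assay error and capping is artefact. The question also bears on SAP 5.8.1.4.1, where seroresponse for a baseline above LLOQ requires at least a 4-fold rise. This stands as a reason to keep the plot. It does not rescue the bare coefficient, because the SAP gives neither that purpose nor a reference value, and a negative value does not separate no relation from a positive relation with slope below 1.

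Other outputs help the reader. Geometric means of actual values and of fold increases are planned with CIs, results are split by baseline serostatus, and seropositive adolescents are set beside seropositive young adults. That lowers the risk of misreading without removing it.

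The Spearman link is inferred. The scatterplots named in SAP 5.8.1.4.1 compare one assay with another, and further details are left to the Data Presentation Specifications. The list is not exhaustive and the SAP 5.6 bullet sits under a correlation heading, so a coefficient is likely but its form is not certain.

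A reader might infer that the shared term forces a negative value whatever the biology. It does not: the sign depends on whether the slope is below 1. A reader might also infer that the value must be strong. That depends on an SD ratio and a seropositive share that the documents do not give.

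**Conclusion.** The point holds as a minor one. The planned coefficient is negative for any slope of log post-vaccination titre on log baseline below 1, including 0, and the SAP says nothing to guard against misreading it. With no relation, Spearman is about -0.43, -0.69 and -0.89 at SD ratios of 0.5, 1 and 2. It is nearer to -0.2 if only about 5% of participants have a baseline above LLOQ, and undefined in seronegatives. These sizes rest on assumed spreads and approximately normal log titres.

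It would be wrong to infer that dose selection or a primary result is at risk. The analysis is exploratory, SAP 2 plans no formal testing, and the correlation endpoint in SAP 1.1 and in protocol section 3 is S-ELISA against VNA only. The documents do not say that this coefficient will be used to judge the effect of prior immunity; that is a risk of interpretation.

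**What to change.** For this bullet in SAP 5.6, report the association of log10 post-vaccination S-ELISA (Day 29 and Day 71) with log10 baseline S-ELISA, by dose level and regimen. Give the Spearman coefficient and the slope with its CI, and state that the slope is read against 0 (no relation) and 1 (constant fold rise).

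Restrict it to participants with baseline S-ELISA above LLOQ. Baseline seropositivity is not the right restriction, because SAP 5.8.4 also counts as seropositive those positive only by N-ELISA, whose S-ELISA is at or below LLOQ.

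If the plot of baseline against fold increase is kept, for example to help read the 4-fold seroresponse definition, show it without a coefficient or with a footnote that its no-relation value is not zero.

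The cost is SAP wording and a few more output lines from the same data. One limitation should be stated: assay error in baseline pulls the slope towards 0, so a slope somewhat below 1 is not by itself evidence against a constant fold rise.

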5.7.1. Adverse Events

5.7.1.1. Definitions

Solicited AEs are used to assess the reactogenicity of the study vaccine and are predefined local events (pain/tenderness, erythema, and swelling at the injection site) and systemic events (fatigue, headache, nausea, and myalgia, fever) for which the participant or parent(s)/caregiver(s) is specifically questioned, and which are noted by participants or parent(s)/caregiver(s) in their reactogenicity diary. Unsolicited AEs are all AEs for which the participant or parent(s)/caregiver(s) is not specifically questioned.

MAAEs are defined as AEs with medically-attended visits including hospital, emergency room, urgent care clinic, or other visits to or from medical personnel for any reason. Routine study visits will not be considered medically-attended visits. New onset of chronic diseases will be collected as part of the MAAEs. MAAEs are to be reported for all participants from the first vaccination until 6 months after each vaccination, except for MAAEs leading to study discontinuation which are to be reported during the entire study.

Solicited AEs shown in the tables are extracted from the investigator assessment pages (CE) of the CRF. Solicited administration site symptoms will by definition be considered as related to the study vaccine.

The following adverse events of special interest (AESI) will be collected in this study:

- Thrombosis with Thrombocytopenia Syndrome (TTS), defined as:
 - Thrombotic events: suspected deep vessel venous or arterial thrombotic events as detailed in CTP Section 10.14 and in Section [6.10](#)
 - Thrombocytopenia, defined as platelet count below 150,000/ μ L.
- Multisystem Inflammatory Syndrome in Children (MIS-C), defined as:
 - An individual aged <21 years presenting with fever^a, laboratory evidence of inflammation^b, and evidence of clinically severe illness requiring hospitalization, with multisystem (≥ 2)

^a Fever $>38.0^{\circ}\text{C}$ for ≥ 24 hours, or report of subjective fever lasting ≥ 24 hours.

^b Including, but not limited to, one or more of the following: an elevated C-reactive protein (CRP), erythrocyte sedimentation rate (ESR), fibrinogen, procalcitonin, D-dimer, ferritin, lactic acid dehydrogenase (LDH), or interleukin 6 (IL-6), elevated neutrophils, reduced lymphocytes, and low albumin.

- organ involvement (cardiac, renal, respiratory, hematologic, gastrointestinal, dermatologic, or neurological); AND
- No alternative plausible diagnoses; AND
 - Positive for current or recent SARS-CoV-2 (COVID-19) infection by RT-PCR, serology, or antigen test; or COVID-19 exposure within the 4 weeks prior to the onset of symptoms.

The AESI will be reported from the moment of vaccination until the end of the study/early withdrawal. An AESI Adjudication Committee with appropriate expertise will be established to evaluate each suspected AESI and determine cases of TTS.

5.7.1.2. Severity Criteria

All AEs and laboratory data will be coded for severity using a modified version of the FDA grading table, based on the version of September 2007 (US DHHS FDA CBER 2007), included in [Sections 6.8 and 6.9, Toxicity Grading Scale in Adolescents \(12 to 17 Years of Age\)](#).

For AEs not identified in the grading table, the guidelines in CTP (Section 10.4.3) will be applied.

The severity of solicited signs and symptoms are graded in the reactogenicity diary by the participant based on the severity assessment provided in the reactogenicity diary and then verified by the investigator using the Toxicity Grading Scale. The severity of a measured event is derived from the diameter [for erythema and swelling] or the temperature measurements [for fever].

5.7.1.3. Analysis of Adverse Events

The number and percentage of participants with at least one particular AE (unsolicited/solicited) will be tabulated.

Unsolicited AEs will be summarized by System Organ Class and Preferred Term. Solicited AEs will be summarized by class (administration site, systemic) and preferred term.

For solicited AEs, the following tables will be provided: summary, by worst severity grade, at least grade 3, related (systemic only), at least grade 3 related, time to onset (in days) from the start of each vaccination period and duration (in days) for most frequent events (>5%) and body temperature. Note: Duration is defined as number of days from the start of the event until resolution of the event. The time to first onset is defined as (date of first onset – reference date + 1). The reference dates are the start dates of all prior vaccination periods (i.e. the prior vaccination dates for dose 1, dose 2 and/or Booster).

For unsolicited AEs, the following tables will be provided: summary table (including SAE, AESIs, MAAEs, MAAEs leading to study discontinuation, fatal outcome, and discontinuation), all events, most frequent (>5%), at least grade 3, related, at least grade 3 related, and SAE. The proportion of AEs resulting in a medically attended visit (other than routine health maintenance visits) will also be tabulated.

Selected tables will be repeated by SARS-CoV-2 by serostatus at baseline [or in seronegative subgroup only if there are less than 5% of seropositive subjects], and overall.

Listings and/or participant narratives will be provided as appropriate, for those participants who die, discontinue study due to an AE, experience a SAE, or AESI.

